2.1. Multiplicity Adjustment

Treatment comparisons will be performed for the primary objective at the full significance level of 0.05. No multiplicity adjustments will be made for the analysis of secondary and exploratory objectives.

3. Analysis Sets

This table defines the analysis population and datasets for the purposes of analysis.

Population	Description		
Screened	All participants who sign the ICF.		
Randomized	All participants who are randomly assigned to a treatment arm.		
Full Analysis Set (FAS)	All data for patients who are randomized, take at least 1 dose of study		
	medication, and are not discontinued from the study due to inadvertent		
	enrollment. Participants will be analyzed according to the treatment they were		
	assigned.		
Efficacy Analysis Set (EAS)	Data for patients who are randomized, take at least 1 dose of study		
	medication, and are not discontinued due to inadvertent enrollment. Excludes		
	data after permanent discontinuation of study drug (for analysis post–Day 180		
	participants will be analyzed according to the treatment they were assigned) or		
	after new initiation of medications that are known to impact Lp(a) levels.		

Abbreviation: ICF = informed consent form.

4. Statistical Analyses

4.1. General Considerations

Statistical analysis of this study will be the responsibility of Lilly or its designee. Some analyses and summaries described in this analysis plan may not be conducted if not warranted by data (for example, too few events to justify conducting an analysis). Additional analyses of the data may be conducted as deemed appropriate.

Unless otherwise noted, all tests will be conducted at a 2-sided alpha level of 0.05, and confidence intervals (CIs) will be calculated at 95%, 2-sided. All tests of interactions between treatment groups and other factors will be conducted at a 2-sided alpha level of 0.10.

Unless stated otherwise, statistical summaries and analyses will be conducted based on planned randomized treatment group (LY 16 mg 2 doses, LY 96 mg 2 doses, LY 400 mg 2 doses, 400 mg 1 dose plus placebo 1 dose, and placebo 2 doses), regardless of the actual treatment(s) received by the participant. Assessment at or before Day 180 will pool data from both treatment arms assigned to the 400-mg dose.

The primary efficacy assessment, guided by the "treatment-regimen" estimand, which represents the efficacy regardless of treatment discontinuation, will be conducted using the full analysis set (FAS) (Section 3). A restricted maximum likelihood-based, mixed-effect model repeated measures (MMRM) analysis will be used to analyze continuous longitudinal variables. All the longitudinal observations at each scheduled postbaseline visit will be included in the analysis. The model for primary efficacy endpoint of percent change from baseline in Lp(a) will include log(Lp[a])-log(Baseline of Lp[a]) as the dependent variable and the fixed class effects of treatment group (LY 16 mg 2 doses, LY 96 mg 2 doses, LY 400 mg 2 doses, LY 400 mg 1 dose and placebo 1 dose, placebo 2 doses), strata (high risk of cardiovascular events for Lp[a] analysis; high risk of cardiovascular events and Lp[a] strata for non-Lp[a] biomarkers analyses), visit, and treatment-by-visit interaction, as well as the continuous, fixed covariate of baseline Lp(a). An unstructured covariance structure will be used to model the within-participant errors. Significance tests will be based on least squares (LS) means and Type III tests. SAS PROC MIXED will be used to perform the analysis. If this analysis fails to converge, the following covariance structures will be tested in order:

- 1. Toeplitz with heterogeneity
- 2. autoregressive with heterogeneity
- 3. compound symmetry with heterogeneous variances
- 4. Toeplitz
- 5. autoregressive, and
- 6. compound symmetry without heterogeneous variances.

The first covariance structure that converges will be used. The Kenward-Roger approximation will be used to estimate denominator degrees of freedom. Comparisons of difference in time-averaged response from baseline for each treatment group of LY3819469 versus placebo reference group will be made by using contrasts of LS means.

Unless specified otherwise, safety assessments will be guided by an estimand comparing safety of LY3819469 doses with placebo irrespective of adherence to intervention. Thus, safety analyses will be conducted using the FAS (Section 3).

Baseline is defined as the last nonmissing measurement recorded on or before the randomization visit, prior to the first dose of intervention, unless otherwise specified. Data may exist at visits where the variable was not scheduled to be collected. In these situations, data from the early discontinuation visit that does not correspond to the planned collection schedule will be excluded from the MMRM, analysis of covariance (ANCOVA), or logistic regression analysis.

Multiple imputation will be used to impute corresponding missing potential outcome according to the missingness pattern. Table EZEB.4.2 summarizes the strategy to handle ICEs and the imputation method to handle missing values for efficacy endpoints.

For continuous measures, summary statistics will include sample size, mean, standard deviation (SD), median, minimum, and maximum for the actual, the change from baseline and percent change from baseline measurements. LS means and standard errors derived from the analysis (MMRM or ANCOVA) models will also be displayed for the change from baseline measurements. Treatment comparisons will be displayed showing the treatment difference LS means and the 95% CIs for the treatment differences, along with the p-values for the treatment comparisons. For categorical measures, summary statistics will include sample size, frequency, and percentages. A logistic regression model will be used to examine the treatment difference in binary efficacy outcomes with missing endpoints imputed. Fisher's exact test or Pearson's chi-square test will be used for treatment comparisons in other categorical outcomes.

For Lp(a), only nmol/L will be reported because there is no direct conversion to conventional (CN) units. For other laboratory values, both CN and the International System of Units (SI) units will be presented.

Endpoints that compare treatment groups based on percent change from baseline will be conducted by log-transformation of the dependent variables. Standard errors and 95% CIs will be constructed using the delta method. The LS means and standard error for each treatment, difference in LS means between arms, and corresponding 95% CIs will be calculated as shown in Table EZEB.4.1, where Z_b is the baseline of the log of the response.

Table EZEB.4.1.	Summary of Reported Quantities for Variables Requiring Log-
	Transformation

Quantity		Change from Baseline	Percent Change from Baseline	
Within Treatment	Estimate	$\left[\exp\left(\hat{\mu}_{\Delta \mathbf{Z},k}\right) - 1\right]\exp(\bar{Z}_{b})$	$\left[\exp(\hat{\mu}_{\Delta \mathrm{Z},k})-1 ight] imes 100$	
	SE	$\exp(ar{Z}_{b\cdot})\exp(\hat{\mu}_{\Delta Z,k})\cdot\widehat{SE}_{\Delta Z,k}$	$\exp(\hat{\mu}_{\Delta Z,k}) \cdot \widehat{SE}_{\Delta Z,k} imes 100$	
	p-value	NR	p_k	
	Estimate	$[\exp(\hat{\mu}_{\Delta Z,k}) - \exp(\hat{\mu}_{\Delta Z,R})] \cdot \exp(\bar{Z}_{b})$	$(\exp(\hat{\mu}_{\Delta Z,k \ vs \ R}) - 1) \times 100$	

Quantity		Change from Baseline	Percent Change from Baseline	
Between- Treatment Difference (Treatmen	SE	$e^{\bar{Z}_{b}}\sqrt{e^{2\hat{\mu}_{\Delta Z,k}}\cdot\left(\widehat{SE}_{\Delta Z,k}\right)^{2}+e^{2\hat{\mu}_{\Delta Z,R}}\cdot\left(\widehat{SE}_{\Delta Z,R}\right)}$	$\exp(\hat{\mu}_{\Delta Z,k\ vs\ R})\cdot\widehat{SE}_{\Delta Z,k\ vs\ R}\times 100$	
Reference	p-value	NR	$p_{\Delta Z,k \ vs \ R}$	
Ailii)	95% CI	Estimate $\pm \Phi^{-1}(1-\frac{\alpha}{2})$ *SE	$([\exp(L_{\Delta Z,k vs R}) - 1] \times 100, [\exp(U_{\Delta Z,k vs R}) - 1] \times 100)$	

Abbreviations: CI = confidence interval; NR = not reported; SE = standard error.

In general, a time-averaged parameter will refer to the AUC constructed using the trapezoidal rule, applied to the parameter according to the scheduled time, divided by the length of observation. For example, a time-averaged dependent variable for Days 60 to 180 will equal *AUC*/120, where *AUC* represents the AUC constructed by the trapezoidal rule.

Details about the analyses regarding demographic and baseline characteristics, historical illnesses, and preexisting conditions, treatment compliance, concomitant medications, and important protocol deviations can be found in Appendices 1 through 5 (Section 6.1 through Section 6.5, respectively.

While considering treatment-emergent abnormal safety laboratory values and vital signs, the baseline observation period starts from the screening visit and ends prior to or at the randomization visit, wherein all scheduled and unscheduled measurements will be included. Baseline for the corresponding safety analysis will be the maximum/minimum (that is, the most extreme/abnormal) from all these measurements during the baseline period. For postbaseline measurements, all scheduled and unscheduled measurements in the analysis period will be included. Table EZEB.4.3 summarizes the definition of baseline, postbaseline, and patient population for different safety endpoints.

End of study participation for a participant will be the earliest of date of death or date of withdrawal from further participation in the study. For participants considered to be lost-to-follow-up, end of study participation will be the date of lost-to-follow-up reported by the investigator. Participant data included in the database after the last date of study participation will be excluded from statistical analysis.

Statistical treatment comparisons will only be performed between LY3819469 and placebo. Because the trial is not adequately powered to detect differences among LY3819469 doses, comparisons across LY3819469 doses will not be performed unless otherwise specified.

Not all analyses described in this SAP will necessarily be included in the clinical study report (CSR). Any analysis described in this SAP and not provided in the CSR will be available upon request.

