# 9.2. Analyses Sets

Population	Description
Screened	All participants who sign the ICF.
Randomized	All participants who are randomly assigned to a treatment arm.
Full Analysis Set (FAS)	All data for patients who are randomized, take at least one dose of study
	medication, and are not discontinued due to inadvertent enrollment.
	Participants will be analyzed according to the treatment they were assigned.

This table defines the analysis population and datasets for the purposes of analysis.

Abbreviation: ICF = informed consent form.

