#### 9.3.5. Safety Analyses

Safety assessments will be guided by an estimand comparing safety of LY3819469 doses with placebo irrespective of adherence to intervention. Thus, safety analyses will be conducted using the FAS. Safety assessments may also pool the 2 LY3819469 400-mg treatment groups, where appropriate.

AEs will be coded from the actual term using the Medical Dictionary for Regulatory Activities (MedDRA) and reported with preferred terms and system organ class. Selected notable AEs of interest may be reported using high-level terms or Standardized MedDRA Queries.

Summary statistics will be provided for incidence of

- treatment-emergent adverse events (TEAEs)
- SAEs
- study discontinuation due to AEs
- intervention discontinuation due to AEs
- deaths, and
- other cardiovascular endpoints.

Counts and proportions of participants experiencing AEs will be reported for each treatment group, and Fisher's exact test will be used to compare the treatment groups.

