4.8. Safety Analyses

Unless specified otherwise, safety assessments will be guided by an estimand comparing safety of LY3819469 doses with placebo irrespective of adherence to intervention. Thus, safety analyses will be conducted using the FAS. Safety assessments may also pool the 2 LY3819469 400-mg treatment groups, where appropriate.

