4.8.2. Adverse Events

A TEAE is defined as an event that first occurred or worsened in severity after first dose. The Medical Dictionary for Regulatory Activities (MedDRA) low level term (LLT) will be used in the treatment-emergent derivation. The maximum severity for each LLT during the baseline period including ongoing medical history will be used as baseline severity. Events with a missing baseline severity will be treated as "mild" in severity for determining treatment-emergence. Events with a missing severity during the postbaseline period will be treated as "severe" and treatment-emergence will be determined by comparing to baseline severity.

For events occurring on the day of first taking study medication, the case report form collected information (for example, treatment emergent flag, start time of study treatment and event) will be used to determine whether the event was pre- versus post-treatment if available. If the relevant information is not available, then the events will be counted as posttreatment.

The counts and percentages of participants with TEAEs will be summarized by treatment using MedDRA preferred terms (PTs) nested within system organ class (SOC). Statistical comparisons will be applied at both the SOC and PT levels. Events will be ordered by decreasing frequency within SOC. The SOC will be in alphabetical order. For events that are sex-specific, the denominator and computation of the percentage will include only participants from the given sex.

An overview of the number and percentage of participants who experienced a TEAE, a serious adverse event (SAE), or death, participants who discontinued from study treatment or study due to an AE, and relationship to study drug will be summarized by treatment.

The counts and percentages of patients with TEAEs by maximum severity will be summarized by treatment using MedDRA PT. For each participant and TEAE, the maximum severity for the MedDRA PT is the maximum postbaseline severity observed from all associated LLTs mapping to the MedDRA PT. The maximum severity will be determined based on the nonmissing severities. If all severities are missing for the defined postbaseline period of interest, it will show as missing in the table.

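### Safety tables group participants by assigned arm whatever they received, so an active/placebo dosing error would put drug-exposed events in the placebo column

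*SAP*

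**What the plan says.** SAP 4.1 gives the general rule: "Unless stated otherwise, statistical summaries and analyses will be conducted based on planned randomized treatment group", followed by "regardless of the actual treatment(s) received by the participant". It is not specific to safety, but it reaches safety in two steps.

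- **Analysis set.** Protocol 9.3.5 says "Thus, safety analyses will be conducted using the FAS"; SAP 4.1 and 4.8 say the same.
- **Grouping within that set.** Protocol 9.2 defines the FAS and adds "Participants will be analyzed according to the treatment they were assigned". The FAS row in SAP Section 3 matches it.

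The reason given in SAP 4.8 is that "safety assessments will be guided by an estimand comparing safety of LY3819469 doses with placebo irrespective of adherence to intervention".

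No safety subsection states another grouping. SAP 4.8.2 has "The counts and percentages of participants with TEAEs will be summarized by treatment using MedDRA preferred terms (PTs" and further detail, but does not say that treatment means treatment received. Table EZEB.4.3 requires at least one dose but regroups nobody. The hepatic screening plots in SAP 4.8.7.1.1 are labelled by randomized treatment. SAP 4.8.4 refers once to *safety participants*, a population missing from the analysis-set table.

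**The concern.** Keeping people in their assigned arm irrespective of adherence makes sense for participants who stop or who miss the Day 180 dose. It does not settle where to count someone who received a different product. A participant assigned to placebo but injected with LY3819469 is drug-exposed, and an event after that injection is evidence about the drug. Counting it under placebo lowers the drug rate and raises the control rate.

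The control rate matters most here. Matching placebo is pooled for all analyses (SAP 1.2), and statistical comparisons are made only between LY3819469 and placebo (SAP 4.1). One misplaced event in the placebo column therefore enters every comparison. The sample-size sections of both documents also give the amount of safety data as a reason for the trial's size.

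The protocol treats dosing errors as possible. Active doses differ only in the volume drawn from one 160 mg/mL solution (0.1, 0.6 or 2.5 mL), placebo is saline, and each participant is injected twice (Protocol 6.1). Medication error is listed under events meeting the AE definition (Protocol 10.3.1), and overdose is defined (Protocol 6.7).

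**Working it through.** **Step 1: the plan's own figures.** Inputs from Protocol 9.5 and SAP Section 5: 254 randomized 1:2:2:2:2, 15% dropout, 24 completers at 16 mg and 48 in each other arm.

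- (24 + 4 × 48) / (1 − 0.15) = 216 / 0.85 = 254.1, which agrees with 254.
- 254/9 × 0.85 = 24.0 and 254 × 2/9 × 0.85 = 48.0 completers, as stated.
- Power for a 70-point difference with SD 20 is about 100% for both 48 vs 48 and 24 vs 48, consistent with the stated >99%.

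These figures are not in dispute, and regrouping safety does not change them.

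**Step 2: arm sizes for safety.** Using randomized numbers as an approximation to those dosed:

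- 16 mg: 254/9 = 28.2, about 28.
- 96 mg and placebo: 254 × 2/9 = 56.4, about 56 each.
- Pooled 400 mg (Arms C and D): 254 × 4/9 = 112.9, about 113.

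**Step 3: shift from one misplaced event.**

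- 1/28 = 3.6 points (16 mg).
- 1/56 = 1.8 points (96 mg or placebo).
- 1/113 = 0.9 points (pooled 400 mg).

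**Step 4: effect on the planned test.** Protocol 9.3.5 uses Fisher's exact test. The documents give neither an error rate nor an event rate, so every count below is an assumption. In the first three rows, one or two participants assigned to placebo receive the active dose and have the event, and nobody else on placebo has it. The next two rows add one genuine placebo event.

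| Comparison with placebo | As assigned | p | As received | p |
|---|---|---|---|---|
| 96 mg, one misdosed | 5/56 vs 1/56 | 0.21 | 6/57 vs 0/55 | 0.027 |
| 16 mg, one misdosed | 3/28 vs 1/56 | 0.11 | 4/29 vs 0/55 | 0.012 |
| Pooled 400 mg, two misdosed | 5/113 vs 2/56 | 1.00 | 7/115 vs 0/54 | 0.098 |
| 96 mg, one misdosed, one other placebo event | 5/56 vs 2/56 | 0.44 | 6/57 vs 1/55 | 0.11 |
| 16 mg, one misdosed, one other placebo event | 3/28 vs 2/56 | 0.33 | 4/29 vs 1/55 | 0.046 |

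In all five rows the drug-placebo difference is larger when grouped as received. Whether p crosses 0.05 depends on the assumed counts.

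**Step 5: an error between active doses.** Suppose one of the three events in the 16-mg arm belongs to someone who received a higher dose. As assigned, 16 mg vs placebo is 3/28 vs 1/56, p = 0.11. With that participant removed it is 2/27 vs 1/56, p = 0.25. Here the as-assigned table shows the stronger 16-mg signal, so the direction differs from Step 4.

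**Step 6: errors that change nothing.** A placebo participant given the wrong volume of placebo has no effect, because placebo is pooled. A mix-up between Arms C and D at the first dose has no effect up to Day 180, since both receive 400 mg.

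**The case against.** The strongest reply is that the rule is disclosed, the same in both documents, and harmless unless someone is misdosed. The controls are real: central assignment by IWRS and preparation by an uninvolved third party (Protocol 6.3), and supervised administration with product and identity confirmed before dosing (Protocol 6.4). An error would also leave traces. Overdose requires contact with the medical monitor (Protocol 6.7). Important deviations are listed (SAP 6.5), narratives cover deaths, SAEs and discontinuations of treatment due to AEs (SAP 4.8.3), and the hepatic profile review looks at treatment taken over time (SAP 4.8.7.1.1).

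Most of this stands. The controls make errors uncommon, and a misdosed participant need not go unnoticed. But none of these provisions moves an event from one column of the AE tables to another. Narratives and hepatic profiles cover selected participants, and the exposure summary in SAP 4.8.1 counts one or two doses, not which product was given.

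A reader might infer three stronger things that the documents do not support:

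- **That the plan contradicts itself.** It does not; this is a consistent analysis choice.
- **That misgrouping always hides risk.** Step 5 shows the opposite for a higher-dose recipient counted under 16 mg. Dilution of drug vs placebo comes mainly from active/placebo swaps and underdosing.
- **That a changed conclusion should be expected.** The documents give no error rate, and the p-values in Step 4 move with one extra placebo event.

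**Conclusion.** The point holds in conditional form. As written, a drug-exposed participant assigned to placebo would be counted as placebo in every safety table, and the stated rationale about adherence does not cover that case. The bias from an active/placebo error is towards no drug-placebo difference. Errors between active doses blur the columns without a fixed direction.

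The size is nil with no dosing error. Otherwise it is about 1.8 points of incidence per misplaced event in placebo or 96 mg, 3.6 in 16 mg and 0.9 in pooled 400 mg. These figures take the randomized arm sizes as denominators; the Fisher results are illustrations on assumed counts. The change is worth making because it is cheap and can be settled before unblinding.

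**What to change.** In SAP Section 3, 4.1, 4.8 and Table EZEB.4.3:

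1. Define a safety set of participants with at least one dose, grouped by the treatment regimen actually received. Use it for all safety analyses, and in SAP 4.8.4 in place of the undefined term *safety participants*.
2. State that participants dosed as assigned keep their own group. Arm D, which is 400 mg then placebo by design, then stays separate from Arm C after Day 180. A blanket rule of grouping by highest dose received would merge the two and should not be used.
3. State that events after a participant has received any LY3819469 are never counted under placebo. For a first error at Day 180, events before that dose stay with the treatment received up to then.
4. List every participant whose safety group differs from the assigned arm.
5. Leave the efficacy analyses as assigned.

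The cost is a short SAP edit, one listing and a brief period-specific attribution rule. Safety group sizes may differ slightly from randomized sizes.

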Analysis Type (Analysis Set)	ICE	Strategy to Handle ICE	Assumption for Missingness	Methods to Handle Missing Values at Endpoints
Lipids parameter MMRM (EAS)	"Permanent discontinuation of intervention" and initiation of excluded medications taken during the study or new initiation of Lp(a) modifying medication required to be on a stable regimen prior to treatment per protocol inclusion criteria.	Hypothetical	MAR	Data collected after the ICE will be set to missing. Missing values will be imputed using all nonmissing data (excluding data collected after ICEs) from the same treatment arm.
Lp(a) categorical analyses logistic regression (EAS)	"Permanent discontinuation of intervention" and initiation of excluded medications taken during the study or new initiation of Lp(a) modifying medication required to be on a stable regimen prior to treatment per protocol inclusion criteria.	Hypothetical	MAR	Data collected after the ICE will be set to missing. Missing values will be imputed using all nonmissing data (excluding data collected after ICEs) from the same treatment arm.

Abbreviations: ApoB = apolipoprotein B; EAS = efficacy analysis set; FAS = full analysis set; hsCRP= highsensitivity C-reactive protein; ICE = intercurrent event; Lp(a)= lipoprotein(a); MAR = missing at random; MMRM = mixed model repeated measures.

Note: For the continuous analysis of clinical laboratory tests, unscheduled measurements are excluded from analysis to reduce bias. The early discontinuation visits are considered scheduled visits.

Study	Participant Population	Baseline Observations	Postbaseline Observations
Period/Analysis			
Туре			
540 Days Study Per	iod		
1.1) Treatment-	All randomized	The baseline period is defined as	Starts after the first dose of
Emergent Adverse	participants who are	the start of screening and ends	study drug and end of the
Events (FAS)	exposed to at least 1 dose	prior to the first dose of study	study period.
	of study drug	drug (Visit 2).	
1.2) Treatment-	All randomized	Baseline will be all scheduled	Postbaseline will be defined
Emergent	participants who are	and unscheduled measurements	as above (1.1). All scheduled
Abnormal Labs	exposed to at least 1 dose	recorded during the baseline	and unscheduled
and Vital Signs	of study drug who have a	period as defined above (1.1).	measurements will be
(FAS)	normal baseline (with		included.
	respect to the direction		
	being analyzed) and a		
	postbaseline observation		

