4.8.4. Vital Signs

If multiple records of an individual's vital signs are collected at the same visit, they will be averaged prior to being used for data summaries and analyses.

Descriptive summaries by treatment and by nominal visit will be provided for baseline and postbaseline values as well as change from baseline values.

Treatment differences in mean change will be analyzed using the MMRM model as described in Section 4.4.2 for the FAS.

Counts and percentages of participants with treatment-emergent abnormal sitting systolic blood pressure (BP), sitting diastolic BP, and pulse rate will be presented by treatment group. Both planned and unplanned measurements will be included in the analysis. The criteria for identifying patients with treatment-emergent vital sign abnormalities are stated in Table EZEB.4.6.

Table EZEB.4.6.Categorical Criteria for Abnormal Treatment-Emergent Blood
Pressure and Pulse Measurements

Parameter	Low	High
Systolic BP (mm Hg)	≤90 and decrease from	≥129 and increase from
(sitting)	baseline ≥20	baseline ≥20
Diastolic BP (mm Hg)	≤50 and decrease from	≥90 and increase from
(sitting)	baseline ≥10	baseline ≥10
Pulse (bpm)	<50 and decrease from	>100 and increase from
(sitting)	baseline ≥15	baseline ≥15

Abbreviation: BP = blood pressure.

Counts and percentages of participants with maximum systolic BP and diastolic BP will be summarized by treatment groups for the following categories using safety participants.

Systolic BP (mm Hg)	Diastolic BP (mm Hg)
<90	<60
≥90	>60
≥120	>90
≥140	>110
≥160	≥120
≥180	

Abbreviation: BP = blood pressure.

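### Safety analyses use the FAS, which drops dosed participants discontinued for inadvertent enrollment, and two other SAP passages describe a different safety population

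*SAP*

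**What the plan says.** Protocol 9.3.5 and SAP 4.1 and 4.8 all place safety analyses on the FAS. Protocol 9.3.5 reads "Thus, safety analyses will be conducted using the FAS", and SAP 4.1 reads "Thus, safety analyses will be conducted using the FAS (Section 3". Each follows a sentence saying that the safety estimand compares doses with placebo whether or not participants adhere.

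The FAS is narrower than everyone dosed. Protocol 9.2 requires that participants take at least one dose of study "medication, and are not discontinued due to inadvertent enrollment". SAP Section 3 has the same condition with slightly tighter wording: "medication, and are not discontinued from the study due to inadvertent" enrollment. The SAP defines four sets (Screened, Randomized, FAS, EAS), and none is a safety set.

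Two SAP passages describe something else:

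- **Table EZEB.4.3.** SAP 4.1 says: "Table EZEB.4.3 summarizes the definition of baseline, postbaseline, and patient population for different safety endpoints". The population column admits randomized participants "exposed to at least 1 dose" of study drug. Some rows add a baseline or postbaseline data requirement, but none mentions inadvertent enrollment. Every row is nevertheless labelled FAS.
- **SAP 4.8.4, Vital Signs.** Mean changes "will be analyzed using the MMRM model as described in Section 4.4.2 for the FAS", but maximum blood pressure is summarized "for the following categories using safety participants". That term is defined nowhere.

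**The concern.** A safety population normally includes everyone exposed. A participant found ineligible after dosing has still been exposed, and adherence has nothing to do with eligibility, so the stated estimand gives no ground for leaving that person out. Some eligibility limits in protocol 5.2 concern liver enzymes, bilirubin and eGFR. An ineligible participant who was dosed could therefore be one whose laboratory course is of interest; this is an inference, not a documented case.

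Two things are at stake. First, safety and exposure tables could be incomplete for exposed participants. This includes the liver-injury screening plots, which SAP 4.8.7.1.1 says exist to pick out individuals for further review and which Table EZEB.4.7 places on the FAS. Second, the denominator is not settled: following Section 3 and following the population column of Table EZEB.4.3 can give different counts, and *safety participants* gives no rule at all.

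**Working it through.** The main check compares definitions.

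| Place in the plan | Population | Inadvertent-enrollment exclusion? |
|---|---|---|
| Protocol 9.2, FAS | Randomized, at least one dose | Yes: discontinued |
| SAP Section 3, FAS | Randomized, at least one dose | Yes: discontinued from the study |
| Table EZEB.4.3, row labels | FAS | Yes, through the definition |
| Table EZEB.4.3, population column | Randomized, at least one dose (plus data requirements in some rows) | No |
| SAP 4.8.4, MMRM | FAS | Yes |
| SAP 4.8.4, maximum blood pressure | *Safety participants* | Undefined |
| SAP 4.8.1, exposure; Table EZEB.4.7, liver displays | FAS | Yes |
| SAP 4.2, disposition | Counts everyone dosed | No |
| SAP 4.8.3, narratives | Randomized population | No |

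The FAS and the set of all dosed participants differ by exactly those dosed and then discontinued from the study for inadvertent enrollment. An SAE in such a person would be narrated under 4.8.3 but absent from the overview table in 4.8.2. The dosed count in 4.2 can also exceed the exposure count in 4.8.1.

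**Arm sizes.** Inputs from protocol 9.5 and SAP Section 5: 254 randomized, ratio 1:2:2:2:2 (9 shares), 15% dropout.

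- 16-mg arm: 254/9 = 28.2. Each other arm: 2 × 254/9 = 56.4. Pooled 400 mg: 4 × 254/9 = 112.9.
- Check against the plan: 28.2 × 0.85 = 23.99 and 56.4 × 0.85 = 47.98, matching its 24 and 48 completers. In reverse, (24 + 4 × 48)/0.85 = 254.1.

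**Size of an omission.** Neither document gives a count, so 0 to 3 participants is an assumption.

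- Whole trial: 0/254 = 0% to 3/254 = 1.2%.
- One participant: 1/28 = 3.6% of the 16-mg arm, 1/56 = 1.8% of another arm, 1/113 = 0.9% of pooled 400 mg.
- Chance that at least one of k omitted participants is in the 16-mg arm, if omissions fall in proportion to allocation: 1 − (8/9)^k = 11.1%, 21.0% and 29.8% for k = 1, 2 and 3.

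**Upper-end illustration.** Suppose the omitted participant had the group's only case of some event (exact Clopper-Pearson 95% intervals):

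| Group | All dosed | FAS |
|---|---|---|
| 16 mg | 1/28 = 3.6% (0.09% to 18.35%) | 0/27 = 0% (0% to 12.77%) |
| Pooled 400 mg | 1/113 = 0.9% (0.02% to 4.83%) | 0/112 = 0% (0% to 3.24%) |

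The intervals overlap widely. What changes is whether the case appears, not a statistical conclusion.

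**The case against.** The strongest reply is that the exclusion may never apply and would not be hidden if it did.

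- **Rarity.** Eligibility is confirmed before the first dose (protocol 1.3), waivers are barred (protocol Section 5) and discontinuation is expected to be uncommon (protocol 7.2). Protocol 7.1 and 7.2 do not list inadvertent enrollment as a reason to discontinue, though 7.2 allows withdrawal for administrative reasons. Under 7.1, someone who only stops study drug stays in the study and so, on the SAP wording, in the FAS. The SAP version history logs a clarification of the FAS definition in version 2. All of this stands and keeps the point small.
- **Visibility.** SAP 4.2 identifies everyone who discontinues, with reasons; Appendix 3 lists discontinuations and Appendix 5 lists important deviations for all randomized participants. Deaths, SAEs and treatment discontinuations due to AEs are narrated. These make an omission traceable. They do not return the person's other adverse events, laboratory values, vital signs or exposure to the tables.
- **Liver cases.** Protocol 8.2.3 triggers monitoring and evaluation during the trial regardless of analysis set, and the participant profiles in Table EZEB.4.7 carry no FAS label. So the screening plot is not the only route to a case, although it could still be incomplete.
- **Table EZEB.4.3.** The FAS label can be read as governing and the column as shorthand. That is fair, but it leaves the exclusion in force and the term in 4.8.4 undefined.
- **Disposition versus exposure.** A participant-flow count and an analysis-set count may legitimately differ. This is a consequence of the rule, not a separate contradiction.
- **A narrower remedy.** Protocol and SAP agree on the FAS, so a new set creates a departure that must be logged. Replacing the undefined term and listing dosed participants outside the FAS would settle the wording, but the tables would still be incomplete.

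**Conclusion.** The concern holds, as a point to consider. Protocol and SAP put safety analyses on a set that by definition omits some exposed participants, the stated rationale does not support that, and two SAP passages do not match the set. Confidence is high on the definitions and the mismatch, and low on whether anyone is affected.

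The size rests on the assumed range of 0 to 3 participants, at most 1.2% of the trial. A single omission weighs most in the 16-mg arm. The conclusion is limited to completeness of safety and exposure reporting and a clear denominator. The sample size, power and efficacy analyses are untouched, and no direction of bias between arms is implied.

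**What to change.** Add a Safety Analysis Set to SAP Section 3: all randomized participants who received at least one dose, regardless of eligibility or later discontinuation, grouped as assigned as the plan already states. This is in substance the population column of row 1.1 of Table EZEB.4.3.

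Use it in SAP 4.1, 4.8, 4.8.1 and 4.8.4 (in place of *safety participants*) and in Tables EZEB.4.3 and EZEB.4.7. Record the departure from protocol 9.2 and 9.3.5 in SAP 4.11, which now lists only the added Lp(a) time periods. Keep the FAS for efficacy.

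The cost is one analysis-set row, one population flag, relabelled safety tables and one line in SAP 4.11. No new data are needed, and if nobody is affected the results do not change.
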